6. Subjects in PTSD-focused psychotherapy may be enrolled if they have been in therapy for 6 weeks prior to randomization.
7. Able to provide written informed consent.
8. Able to read and write English.

Exclusion Criteria:

1. Subjects with a diagnostic history of schizophrenia or schizoaffective disorder as confirmed by the Mini-International Neuropsychiatric Interview (MINI) 7.0 for DSM-V.
2. Subjects with a history of antidepressant-induced hypomania or mania.
3. Subjects currently exhibiting psychotic features or meeting criteria for current manic, hypomanic, or mixed episode as confirmed by the MINI 7.0 for DSM-5.
4. Current, ongoing serious suicidal risk as assessed by evaluating investigator.
5. Moderate severity or greater Substance Use Disorder (excepting Alcohol Use Disorder) during the 3 months prior to randomization, as determined by the MINI 7.0 for DSM-5. Alcohol Use Disorder may be allowed based on the judgment of study physician/APRN/clinician that patients can remain sober for all study visits.
6. Subjects on a prohibited medication (see Table 1). Patients will not be taken off medication for the purpose of this study.
7. Any history or signs of serious medical or neurological illness. A subject with a clinical abnormality may be included only if the study clinician considers the abnormality will not introduce additional risk factors and will not interfere with the study procedure.
8. History of traumatic brain injury (TBI) with loss of consciousness for more than 24 hours or posttraumatic amnesia for more than 7 days may be considered if the trauma occurred more than 1 year ago, and no more than minimal symptoms have persisted over the past year.
9. Breathalyzer showing an alcohol level > 0% at screening, or at the discretion of the investigator, prior to any study drug infusion.
10. Any history indicating dementia or mental retardation as determined by psychiatric interview.
11. Known sensitivity to ketamine as determined by the study clinician.
12. At screening, resting blood pressure (sitting or supine) lower than 90/60 or higher than 150/90, or resting heart rate lower than 45/min or higher than 100/min.

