20. Mini-International Neuropsychiatric Interview (MINI 7.0): The MINI 7.0 is a short, structured clinical diagnostic interview designed for DSM-V that covers all psychiatric disorders. It is widely used in epidemiological studies and multi-site clinical trials.
21. Montgomery-Asberg Depression Rating Scale (MADRS): The MADRS is a standardized clinical assessment instrument to ascertain depressed mood and neurovegetative signs and symptoms of depression.
22. Pain as the Fifth Vital Sign Numeric Rating Scale (Pain-NRS): The numeric pain score utilized in the VA's Pain as the Fifth Vital Sign initiative relies on an 11-point NRS measure with standardized anchors (0 = "no pain" and 10 = "worst pain imaginable"). Our brief, 3-item measure assesses current pain level, average pain in the past week, and worst pain in the past week.
23. Patient Health Questionnaire-9: This is a 9-item self-report tool for assessing and monitoring depression severity. It is widely used in primary care settings.
24. Patient Reported Outcomes Measurement Information System (PROMIS) Sleep Disturbance and Sleep-Related Impairment short forms: This subscale of the PROMIS is a self-report measure assessing sleep disturbance and sleep-related impairment during the past-week.
25. Positive and Negative Symptom Scale (PANSS): The PANSS is commonly used to measure the severity of symptoms in psychotic disorders. It is a clinician-administered scale and includes three categories of symptoms: (1) positive symptoms, such as hallucination and delusion; (2) negative symptoms, such as flat affect and difficulty in abstract thinking; (3) general psychopathology, such as mannerisms and posturing.
26. PTSD Checklist (PCL-5): The PCL-5 is a 20-item self-report measure of the core diagnostic symptoms of PTSD, as described in the DSM-5 for Mental Disorders. The PCL-5 shares similar reliability with the CAPS-5 and has a variety of purposes, including: screening for PTSD symptoms, diagnosing PTSD and monitoring symptom change during and after treatment.
27. Quick Drinking Screen (QDS) Self-Report Version: The QDS is a 4-item measure of alcohol consumption that probes frequency and quantity of consumption.

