
Medical Assessments:

1. Physical exam and health assessment by a licensed physician or Advanced Practice Registered Nurse (APRN).
2. Routine laboratory studies, including: a comprehensive metabolic panel (e.g. electrolytes, hepatic and renal function tests), C-reactive protein (CRP), erythrocyte sedimentation rate (ESR), and urinalysis. Additional tests will be requested as clinically indicated.
3. Breathalyzer tests will be performed at screening and on test days. The results will be determined before proceeding with any infusions.
4. An ECG.
5. A serum/urine pregnancy test will be administered to all reproductive age females enrolled in the study prior to participation and will be repeated pre-infusion on test days.

Length of Assessment Procedures: It is estimated the screening visit to determine subject eligibility will take 6-7 hours. The CAPS-5 interview will take approximately 1 hour, additional clinician-administered assessments may take up to 20 minutes each. Infusion visits will take approximately 6-7 hours, including assessments, any required medical procedures, the infusion, and post-infusion observation. Follow up visits may take 3-7 hours, depending on which

visit and the requirements (see Table 2 for visit requirements). Some visits may take place over more than one day during the study week, depending on the subject's needs.

Study Drug Administration: Subjects will complete 1-2 infusions per week since test days (i.e. ketamine/placebo infusions) will occur at intervals of no less than 2- and no more than 7-days apart. Following an overnight fast, subjects will receive either 0.9% saline, ketamine 0.2 mg/kg, or ketamine 0.5 mg/kg depending on randomization assignment. All study drugs will be intravenously administered and infused over approximately 40 minutes. Randomization will be stratified by study site (i.e. West Haven and San Antonio) and alcohol use disorder comorbidity.

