Primary specific aim: To test the dose-related effects of ketamine on PTSD symptoms in Veterans and active duty military population. We will follow our prior PTSD clinical trial,⁵ using mixed effects regression models, with group, time, group by time effects for the primary outcome variable (PCL-5). We will stratify by infusion center and alcohol use comorbidity. We do not expect to observe significant differences in treatment effects by infusion center but we will test the interaction of treatment group and infusion center and perform follow-up analyses by site as necessary. Similarly, we do not expect significant moderating effects of alcohol use comorbidity but will assess the interaction between treatment and alcohol use comorbidity and perform follow-up tests as necessary. This approach will be applied to most secondary outcome measures as well. Mixed effects regression models use all available data on each subject, are flexible in modeling the correlation structure of the data and give unbiased results under missing at random assumptions. We will select the best-fitting correlation structure for the primary and each secondary outcome based on Schwarz-Bayesian Information Criterion (BIC). Time will be considered as a categorical predictor and post-hoc tests between groups will be conducted for the change from baseline to end-point, which is of primary interest. To assess the trajectory of ketamine effects over time, we will test for linear, quadratic and higher order time trend differences. Post-hoc tests will also be performed to assess whether dose effects are linear. Change in PTSD symptoms is expected to be the largest for the higher dose ketamine group. However, it is possible that the change in the higher dose ketamine group is not significantly different from the change in the lower dose ketamine group. Thus, we will also estimate effect sizes with confidence intervals for the change from baseline to end-point in each group and use this information together with safety data to inform dose selection for potential future studies of ketamine efficacy and evaluation of mechanism of action in PTSD.

In addition to testing the potential moderating effect of comorbid alcohol use described above, we will also perform exploratory analyses to assess moderating effects of depression, medication

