Exploratory aim 1: Safety of repeated ketamine exposure. 1) Changes in psychotic (PANSS), dissociative (CADSS) and cognitive symptoms (Cogstate) across time between groups will be assessed using mixed effects regression models with group as between-subject factor and time as a within-subject factor as described in the primary specific aim. We anticipate significant differences between ketamine and placebo during infusions but no significant between-group differences at discharge and at the two-week and one month follow-up. 2) Descriptive statistics will be calculated for consumption of recreational substances prior to randomization, throughout the trial and for 4 weeks following the last ketamine exposure. If sufficient sample size is available for analytic modeling of recreational substance use between groups, mixed effects models or nonparametric regression will be used to test for differences between groups. 3) Breath alcohol levels over time will be compared as described for Aim 1. 4) Descriptive statistics will be calculated to summarize types and rates of adverse events between groups. Rates of adverse events will be compared using Fisher's exact tests since numbers of adverse events per arm may be small. Exact logistic regression analyses will be used to assess effects of additional potentially confounding covariates on adverse events if possible (i.e. if sufficient numbers of adverse events are present in the sample to allow for such analysis).

Exploratory aim 2: To assess the durability of ketamine effects on PCL-5, we will use mixed effects regression models in the subjects who responded to the study drug by the end of the double-blind treatment. Week post-treatment will be a within-subject factor and the treatment group a between-subject factor in this analysis, and we will covary for severity at the end of treatment. We will perform pairwise comparisons over time to determine if subjects maintain improvements on ketamine during the 4-week follow-up.

Exploratory aim 3: To test the clinical significance of PCL-5 changes, we will perform secondary mixed model analyses on CAPS-5, CGI, VR-12, PROMIS, WHYMPI, and Pain-NRS, using the same approach as described in Aim 1.

Exploratory aim 4: To test the integrity of the blind, we will use chi-square tests and ANOVA models to compare the accuracy and level of confidence in the guessed treatment assignment between groups.

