Screening: The risks and discomforts of the screening and evaluations are minimal. No discomfort is expected to be associated with the physical examination or the intake interview with the study clinician, other than the possible stress of answering personal questions and the risk of loss of privacy and confidentiality, while revealing personal information. Subjects will be answering questions about their symptoms and filling out questionnaires. They may find this process to be inconvenient, uncomfortable or upsetting. The psychological interviews may include personal questions about previous experiences. The questions will be asked in a private room. Subjects will be informed that they do not have to answer any question that they do not want to answer. Subjects will also have the option to discuss their concerns with someone on the research staff. One or more trained individuals will be available to talk to the subjects should they become distressed during an interview or while filling out questionnaires. These assessments have been used without difficulty or adverse events in our previous studies with a similar population. The major disadvantage is the time taken to complete them. Our past experience with these measures indicates that they are acceptable to patients. Additionally, participants found to have a positive breathalyzer for alcohol or positive urine pregnancy screen prior to any study drug infusion will not be allowed to receive treatment that day. The appointment may need to be re-scheduled or the participant may need to be withdrawn from the study for their safety.

Risks of ECG tests: Sometimes the adhesive pads used to attach the leads for recording the electrical activity of the heart can cause skin irritation. Such irritation usually clears without treatment.

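### The Aim 1 mixed model suits breath alcohol poorly, because entry and dosing checks hold most readings at or near zero, and no analysis names the drinking questionnaire (QDS)

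*Protocol*

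**What the plan says.** Item 1 of the secondary specific aims names breath alcohol, before randomization, during the trial and for four weeks afterwards, as its only alcohol measure. The analysis is in Exploratory aim 1, item 3: "Breath alcohol levels over time will be compared as described for Aim 1". Under the primary specific aim in the Analysis plan, that means a mixed model with group, categorical time and their interaction, a covariance structure chosen by BIC, and this contrast: "post-hoc tests between groups will be conducted for the change from baseline to end-point, which is of primary interest".

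Other parts of the protocol make a zero reading a condition of entry and dosing:

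- Exclusion criterion 9: "Breathalyzer showing an alcohol level > 0% at screening, or at the discretion of the investigator, prior to any study drug infusion".
- Medical Assessments, item 3, on breathalyzer tests: "The results will be determined before proceeding with any infusions".
- Research Risk, Screening: someone positive before an infusion "will not be allowed to receive treatment that day", with no mention of discretion; the visit may be rescheduled or the person withdrawn.
- Exclusion criterion 5 admits alcohol use disorder (AUD) only where the clinician judges that the person can attend every visit sober.
- Problematic drinking during the trial is listed as a reason for discontinuation.

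Drinking between visits is measured separately. Dependent Measures, item 27, states: "The QDS is a 4-item measure of alcohol consumption that probes frequency and quantity of consumption". Table 2 schedules QDS at V1, V2, V7, V11, V14 and V16. Neither the protocol's Analysis plan nor the SAP's Brief Statistical Analysis Plan and Supplemental sections name it in an analysis.

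**The concern.** A comparison of change from baseline needs an outcome that is free to vary at baseline and afterwards. Here the baseline value is a condition of entry, and most on-treatment values are conditions of dosing. What remains is mainly a record of whether people arrived sober at visits where they had been told to be sober. That says little about how much they drank on other days.

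The trial admits people with AUD and stratifies on it, so a reader will look for alcohol-safety evidence. A test that can hardly reject will probably return no difference, and in a safety section that may be read as reassurance. The instrument that does measure frequency and quantity has no stated analysis.

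**Working it through.** The documents give no positive-reading rate, standard deviation or power for breath alcohol, so there is no plan figure to reproduce. Step 1 uses document facts; steps 2 to 4 are illustrations on stated assumptions.

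**Step 1. Count readings from Table 2, leaving out the optional open-label visits.** V1 to V11 gives 11 and V13 to V16 gives 4, so 15 per person. Those tied to entry or an infusion are V1, V2, V4-V6, V7 and V8-V10: 1 + 8 = 9. Those tied to neither are V3, V11 and V13-V16: 6. Through V11, 9 of 11 readings are tied. Both candidates for baseline (screening and the reading before infusion 1) are among the nine. If the checks are applied, baseline is zero for everyone dosed, and change to the end of treatment is simply the V11 reading.

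**Step 2. Share of zeros.** Assume the nine tied readings are zero and that each untied reading is positive with probability p. The share of zeros is 1 − 6p/15. With 53 completers per arm (section IV.A), expected positives per arm are 53p at V11 and 6 × 53 × p = 318p over the six untied visits, if all attend. The chance that no arm has a positive reading at V11 is (1 − p)^159.

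**Step 3. Behaviour of the test.** This was simulated with 20,000 runs: a three-group F test at nominal 5% on change from an all-zero baseline to V11, with no true difference. Positive readings were assumed lognormal (log-SD 0.7), and an all-zero data set counted as no rejection. It is a simplification of the full mixed model.

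| Assumed p | Zeros among 15 readings | Positives per arm, V11 | No positive in any arm, V11 | Positives per arm, six visits | Simulated type I error |
|---|---|---|---|---|---|
| 0.5% | 99.8% | 0.27 | 45% | 1.6 | about 0.1% |
| 1% | 99.6% | 0.53 | 20% | 3.2 | 0.3% |
| 2% | 99.2% | 1.06 | 4% | 6.4 | 1.2% |
| 5% | 98.0% | 2.65 | below 0.1% | 15.9 | 2.8% |

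The test is strongly conservative across the range, so its sensitivity is poor.

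**Step 4. Would an exact test rescue breath alcohol?** At V11, with 53 per arm, two-sided 0.05 and no multiplicity adjustment, Fisher's exact test has about 3% power for 1% against 5%, and 22% for 2% against 10%. Counts are the honest way to report these data, but they do not recover the lost information.

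**Step 5. Where QDS might belong.** Exploratory aim 1, item 2 covers consumption of recreational substances over the same periods, with modelling if numbers allow. It does not mention alcohol, which has its own item 3. The primary-aim text carries the Aim 1 method over to most secondary outcomes, and QDS is in the list of measures under Dependent Measures. Either could apply, and neither says so. Separately, the Day 1 follow-up text lists QDS while Table 2 shows none at V3.

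**The case against.** The strongest reply is that the data are not empty and the plan is not without safeguards. Much of that stands.

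- **Almost every value is zero by design.** A reader might infer this, but the documents do not support it. Six of the 15 readings, including all four weekly follow-ups, decide no infusion. A positive pre-infusion result stops treatment, not recording, and criterion 9 makes that bar discretionary.
- **The model cannot be fitted.** This goes too far. A model with a common variance can be fitted once any reading is non-zero, and the simulation shows a conservative test, not an impossible one. The Analysis plan also allows transformations or non-parametric methods where needed. That fallback is generic, though: no transformation separates tied zeros, and ranks that are mostly tied carry little information.
- **The result would be null whatever participants drink.** This is too absolute, because positives at the untied visits can be compared.
- **QDS data go unused.** This is not established, since either route in step 5 could cover it. What stands is that no analysis names it.
- **Low stakes.** The aim promises only to evaluate breath alcohol, the Analysis plan labels this work exploratory, and no primary conclusion depends on it. That is correct and sets the weight of the point.

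**Conclusion.** The point holds as a minor one about an exploratory safety analysis. The stated method is ill-suited: 9 of 15 scheduled readings, baseline included, are held at or near zero, and the end-of-treatment contrast rests on one untied reading. On the assumed 0.5% to 5% positive rate at untied visits, 98.0% to 99.8% of readings are zero and the nominal 5% test rejects about 0.1% to 2.8% of the time under no difference. Those percentages depend on the assumed rate and on the checks being applied as the Research Risk section describes; the 9-of-15 count comes directly from Table 2. A null breath-alcohol result should not be read as evidence that drinking was unchanged. Whether QDS has a planned analysis is unclear. The criterion 9 and Research Risk statements on positive pre-infusion readings conflict and must be reconciled. The primary PCL-5 result is unaffected.

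**What to change.** Replace item 3 of Exploratory aim 1 with the following:

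1. Tabulate participants with any positive breath reading by arm and visit, compare arms by Fisher's exact test, and state that power is low. The protocol already uses that test for adverse events on the ground of small numbers.
2. State which reading enters the analysis when a positive result leads to a rescheduled infusion.
3. Name QDS frequency and quantity as the alcohol-use safety outcome over V1, V2, V7, V11, V14 and V16, in a count, ordinal or other zero-tolerant mixed model adjusted for site and AUD. Say whether item 2 is meant to include alcohol.
4. Report treatment-phase and follow-up results separately, because V13-V16 come after the optional open-label infusion offered to non-responders.

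The cost is analysis text only, since every measure is already scheduled. QDS is self-report, so under-reporting is possible, and the analysis remains exploratory. The SAP is written in the past tense; if the change is adopted after unblinding, it must be labelled post hoc.

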This is a double-blind, placebo-controlled, 8+ week clinical trial in which patients will be randomized to one of three treatment groups based on the content of their 8 intravenous infusions throughout the study: 0.9% saline (placebo), ketamine (0.2 mg/kg), or ketamine (0.5 mg/kg). On each infusion day, pre-infusion assessment of adverse events and symptom severity will be conducted using a set of clinician- and self-rated scales (see below). Subjects will then receive the ketamine/placebo dose via pump as a 50 mL intravenous infusion administered over 40-minutes based upon randomized treatment assignment. The Research Pharmacy prepares syringes containing 56 mL of drug/placebo (including the 50 mL dose plus 6 mL tubing volume to ensure all the study medication is infused). Possible adverse events (AEs) and mood disturbance symptoms will be assessed repeatedly before, during, and after infusion up to 120 minutes following the study drug administration. At the end of each infusion, clinically significant AEs observed will be recorded in the research record. Subjects will receive 1-2 infusions per week (to assure that no less than 2 calendar days (e.g., Monday & Wednesday; Tuesday & Thursday) and no more than 7 days intervals exist between infusions) for 4+ weeks. A 4-week follow-up period will follow. If an infusion session is missed, it can be made up as long as the 2-day minimum/7-day maximum interval in between sessions is maintained. On each subsequent follow-up visit, possible AE's experienced between visits, will be recorded in the research record. Non-responders (i.e. less than 25% improvement from the baseline CAPS-5 score) at the end of the double-blind treatment period (end of Week 4) will be offered a single infusion of open-label ketamine 0.5 mg/kg. Consistent with the CAP goals, we will collect and bank blood samples at visits 2 (baseline; prior to the first infusion), 3, 7, 11, and 16 for future biomarker analyses.

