## **Brief Statistical Analysis Plan:**

Briefly, the PCL-5 was considered the primary outcome, while CAPS-5 and MADRS were considered secondary measures. The primary analysis used mixed effects models, with group, time, and group-by-time effects. The secondary analyses examined the rapid and sustained effects of ketamine compared to placebo, at 24 hours post-first and post-last infusion, respectively, by focused contrasts in the mixed models. Sustainability of the effects of ketamine on PTSD symptoms was assessed with similar mixed models for PCL-5 and CAPS-5 during the follow-up period; considering that this analysis included only the responders (non-responders received open label ketamine), we covaried for pretreatment symptom severity. However, there was no difference in pretreatment severity and the results are similar without covarying for severity. The dissociative and psychotomimetic effects were examined using comparable mixed models for CADSS and PANSS, while adding interval (30 minutes vs. 120 minutes) and appropriate interactions to the models.

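### The adverse-event comparison names no unit for Fisher's exact test and makes no use of recurrence over up to eight infusions: valid if run on participants, but insensitive for events that are frequent per infusion

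*Protocol*

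**What the plan says.** In Protocol section IV.F, Analysis plan, Exploratory aim 1, item 4 starts with descriptive summaries of adverse events. It then states: "Rates of adverse events will be compared using Fisher's exact tests since numbers of adverse events per arm may be small". It continues: "Exact logistic regression analyses will be used to assess effects of additional potentially confounding covariates on adverse events if possible", the condition being enough events. The unit of analysis is not named.

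The data are repeated by design. Under Research Plan and Study Procedures, "patients will be randomized to one of three treatment groups based on the content of their 8 intravenous infusions throughout the study". The same paragraph says "Possible adverse events (AEs) and mood disturbance symptoms will be assessed repeatedly before, during, and after infusion", and "At the end of each infusion, clinically significant AEs observed will be recorded in the research record". Table 2 schedules adverse-event recording at every visit after screening.

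Other safety measures do get repeated-measures models. Item 1 of the same aim says that psychotic, dissociative and cognitive scores "will be assessed using mixed effects regression models with group as between-subject factor and time as a within-subject factor". The SAP agrees: "The dissociative and psychotomimetic effects were examined using comparable mixed models for CADSS and PANSS". The SAP describes no adverse-event comparison, so item 4 is the only specification.

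**The concern.** Fisher's exact test assumes independent units, and here the randomised unit is the participant. Item 4 speaks of rates and of numbers of events per arm, which leaves two readings open.

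- **Participants with at least one event.** This is valid. But eight exposures push the ever/never proportion towards 100% for any event that is common at a single infusion, so a real difference in frequency between arms can shrink or vanish.
- **Events or infusions.** Repeat events in one participant are then treated as independent, and p-values are too small.

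Neither reading takes account of the number of infusions received. Section IV.A plans for 159 of 198 participants to complete, and intolerable reactions are a listed reason for discontinuation. Exposure may therefore differ between participants for reasons linked to the events themselves. Exact logistic regression as described adds covariates; it does not deal with recurrence.

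Safety of repeated exposure is a stated secondary aim, and the analysis of the primary aim says that safety data will help inform dose selection for future studies. The CADSS and PANSS models do not cover effects such as nausea, vomiting or headache, which section V lists for ketamine.

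**Working it through.** **Inputs from the documents.** About 66 randomised and 53 completing per arm (section IV.A), so non-completion is 1 − 53/66 = 19.7%. Eight infusions. Two-sided tests.

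**Assumptions.** The documents give no adverse-event rate, ICC, error rate or power for this comparison, so there is no plan figure to reproduce. I assume 5% significance per comparison, two arms of 66, ICC from 0.05 to 0.5, and per-infusion rates from 5% to 45%.

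**Step 1: saturation of ever/never.** With independent infusions, P(at least one event) = 1 − (1 − p)^8.

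- 5% v 10% per infusion: 1 − 0.95^8 = 34% v 1 − 0.90^8 = 57%. The contrast survives.
- 20% v 30%: 1 − 0.80^8 = 83% v 1 − 0.70^8 = 94%.
- 30% v 45%: 94% v 1 − 0.55^8 = 99%. The contrast is nearly gone.

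A positive ICC lowers these proportions and weakens the saturation.

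**Step 2: power.** I simulated 3,000 trials per setting. Participant probabilities were beta-distributed with the given mean and ICC. Each participant had 8 infusions, except 19.7% who left after 1–7. Fisher's test on ever/never was compared with a test of per-infusion rates that used infusions received as denominator and a participant-clustered variance.

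| Per-infusion rates | ICC | Fisher, ever/never | Clustered test |
|---|---|---|---|
| 5% v 10% | 0.05 | 61% | 72% |
| 5% v 10% | 0.3 | 40% | 40% |
| 5% v 15% | 0.3 | 89% | 87% |
| 10% v 20% | 0.05 | 82% | 97% |
| 10% v 20% | 0.3 | 68% | 71% |
| 20% v 30% | 0.05 | 40% | 87% |
| 20% v 30% | 0.1 | 42% | 80% |
| 20% v 30% | 0.3 | 40% | 54% |
| 30% v 45% | 0.05 | 30% | 98% |
| 30% v 45% | 0.3 | 47% | 79% |

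Separate runs differ by up to about 3 points. With equal rates in both arms, at 10% or 30% per infusion, the false-positive rate was about 3–4% for ever/never Fisher and 5–6% for the clustered test.

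**Step 3: false positives if events or infusions were the unit.** Approximate design effect DEFF = 1 + 7 × ICC; type I error = 2[1 − Φ(1.96/√DEFF)].

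- ICC 0.1: DEFF 1.7, error 13%.
- ICC 0.3: DEFF 3.1, error 27%.
- ICC 0.5: DEFF 4.5, error 36%.

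Simulation agrees for per-infusion rates of 10% and above: about 11–13%, 23–27% and 32–36%. These are not upper bounds; ICC 0.7 gives DEFF 5.9 and 42%.

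**The case against.** The strongest reply is that counting participants with at least one event is the standard reading and a legitimate safety comparison. It fits the pairing with exact logistic regression and the intent-to-treat statement, and the SAP's own binary outcomes are one per participant. No passage makes the event or infusion the unit. The protocol also chooses Fisher's test because it expects small numbers, which is where ever/never loses little. Descriptive rates will be reported in any case. All of this stands, and it limits the point to an improvement.

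A reader might infer more than the documents support:

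- **That acute effects are compared only by Fisher's test.** They are not. Exact logistic regression is conditionally planned, and dissociative and psychotic effects, measured at every infusion, have mixed models in both documents. Feelings of drunkenness and giddiness, which section V describes as frequent or common, may be picked up largely there. No passage says they will be logged as adverse events at a high share of infusions.
- **That false-positive rates of a quarter to a third are built into the plan.** They would follow only from an event-level or infusion-level test, which is not stated, and only with an ICC near 0.3–0.5.
- **That most of the power is lost for common effects in general.** This needs high per-infusion rates and a low ICC. It cannot be combined with the inflation figure, which needs a high ICC.

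What remains is that item 4 names no unit, ignores infusions received, and has no method for frequent events outside the CADSS and PANSS domains.

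**Conclusion.** The point holds as a minor one. Fisher's test on participants with at least one event is valid and should stay for infrequent events and SAEs. For events that are frequent per infusion, it gives up power that data already being collected could provide: about 14 to 47 points for 20% v 30% per infusion, and about 32 to 68 points for 30% v 45%, for ICC from 0.3 down to 0.05. At a comparator rate of about 5% or less the loss is small or nil (about 11 points for 5% v 10% at ICC 0.05, none at 0.3). At 10% it is small once ICC is 0.3 or more. Naming the unit would also rule out the event-level reading.

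Every size here depends on assumed event rates and ICC. The documents do not support a claim that the safety analysis is invalid, or that it cannot reveal a difference in tolerability between doses. The primary PCL-5 analysis is not touched.

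**What to change.** In Exploratory aim 1, item 4:

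1. State that Fisher's exact test is applied to the number of participants with at least one event, not to event or infusion counts, and keep it for infrequent adverse events and SAEs.
2. For adverse events that prove frequent at the double-blind infusions, add a comparison of per-infusion rates between arms that is clustered on participant. One option is a GEE logistic or log-link count model with robust variance and infusions received as denominator or offset. Fix in advance what counts as frequent.
3. Report the number of infusions received by arm beside these rates, because early stopping may be related to the events.

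The cost is a paragraph of wording and one extra model per frequent event term, with no new data. The model may not converge for sparse terms; the participant-level Fisher test then remains the analysis.
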